5.1.2 Visit 2 – Prospective Baseline Period (Day -28, Weeks -4 to -1)

The following assessments will be conducted at this visit:

- Complete caregiver placebo training
- Record vital signs (pulse rate, BP, temperature, and RR)
- Collect blood samples for hematology and serum chemistry
- Collect urine sample for urinalysis and for pregnancy testing (FOCP only)
- Administer C-SSRS
- Review and record concomitant medications
- Provide Headache Diary training to record daily headache activity/symptoms and rescue medication usage

- Download Headache Diary app on caregivers' phone

5.1.3 Visit 3 (+2 days) – Randomization (Day 1)

The following assessments will be conducted at this visit:

- Review inclusion/exclusion criteria
- Record vital signs (pulse rate, BP, temperature, and RR)
- Collect urine sample for pregnancy test (FOCP only)
- Administer C-SSRS
- Review and record concomitant medications
- Review Headache Diary for eligibility
- Administer PedMIDAS, PedsQL 4.0 scales
- Perform cognitive assessment
- Perform eye exam
- Record AEs
- Randomization
- Dispense SM (4-week supply) and provide instructions for dose titration

5.1.4 Titration Period (Days 1 to 56, Week 1 to end of Week 8)

Intervening Phone Calls

At Days 14 (± 2 days) and 43 (± 2 days) there will be telephone calls to subjects to assess the tolerability of the SM treatment.

The following assessments will be made during these telephone contacts:

- Review and record concomitant medications
- Record AEs
- Provide guidance (as needed) on dose reduction

Visit 4 (Day 29 \pm 7 days)

During Treatment Phase (Visits 4 through 9), sample collection and testing have been specified for respective visits by the Sponsor. Besides the testing specified during these respective visits, repeat testing for clinical laboratory parameters, vital signs, and/or ECG may be permitted, at the discretion of the Investigator. However, these repeat testing will require justification from the site and agreement with the Medical Monitor and the Sponsor on a case-by-case basis prior to conducting the tests.

The following assessments will be conducted at this visit:

- Perform physical examination (excluding genitourinary system) including height and weight, and neurological examination

- Record vital signs (pulse rate, BP, temperature, and RR)
- Collect urine sample for pregnancy test (FOCP only)
- Administer C-SSRS
- Review and record concomitant medications
- Review Headache Diary
- Record AEs
- Collect SM and assess adherence; retrain as needed
- Dispense SM (4-week supply) and review medication instructions with subject and caregiver
- Placebo training refresher

5.1.5 Maintenance Period (Days 57 to 140, Week 9 to the end of Week 20)

Visit 5 (Day 57 ± 7 days)

The following assessments will be conducted at this visit:

- Perform 12-lead ECG
- Record vital signs (pulse rate, BP, temperature, and RR)
- Collect blood samples for hematology and serum chemistry
- Collect urine sample for urinalysis and for pregnancy test (FOCP only)
- Collect urine sample for drug screen
- Administer C-SSRS
- Review and record concomitant medications
- Review Headache Diary
- Administer PedMIDAS, PedsQL 4.0 scales
- Perform cognitive assessment
- Record AEs
- Collect SM and assess adherence; retrain as needed
- Dispense SM (4-week supply) and review medication instructions with subject and caregiver

Visits 6 (Day 85 ± 7 days) and Visit 7 (Day 113 ± 7 days)

The following assessments will be conducted at these visits:

- Perform physical examination (excluding genitourinary system) including height and weight, and neurological examination
- Record vital signs (pulse rate, BP, temperature, and RR)
- Collect urine sample for pregnancy testing (FOCP only)
- Collect urine sample for drug screen
- Perform eye exam (only at Visit 6)
- Administer C-SSRS
- Perform cognitive assessment

- Review and record concomitant medications
- Review Headache Diary
- Record AEs
- Collect SM and assess adherence; retrain as needed
- Dispense SM (4-week supply) and review medication instructions with subject and caregiver
- Placebo training refresher (only at Visit 6)

Intervening Phone Calls

At Days 71 (± 2 days), 99 (± 2 days) and 127 (± 2 days), there will be telephone calls to subjects to assess the tolerability of SM treatment.

The following assessments will be made during these telephone contacts:

- Review and record concomitant medications
- Record AEs
- Provide guidance (as needed) on dose reduction, up to one dose reduction will be allowed for safety and tolerability during this period. Additional dose titration related to body weight changes will be reviewed and approved by the Medical Monitor and the Sponsor on a case by case basis.

5.1.6 Taper Period (Days 141 to 161, Week 21 to the end of Week 23)

Intervening Phone Call

At Day 148 (± 2 days) there will be a telephone call to subjects to assess the tolerability of the SM treatment.

The following assessments will be made during these telephone contacts:

- Review and record concomitant medications
- Record AEs
- Provide guidance (as needed) on dose reduction

Visit 8 (Day 141 \pm 7 days)

The following assessments will be conducted at this visit:

- Perform physical examination (excluding genitourinary system) including height and weight, and neurological examination
- Record vital signs (pulse rate, BP, temperature, and RR)
- Collect blood samples for hematology and serum chemistry
- 
- Collect urine sample for urinalysis and for pregnancy testing (FOCP only)
- Collect urine sample for drug screen
- Administer C-SSRS

- Administer PedMIDAS, PedsQL 4.0
- Perform cognitive assessment
- Review and record concomitant medications
- Review Headache Diary
- Record AEs
- Collect SM and assess adherence
- Dispense 3-week supply of SM and provide instructions for dose tapering

Visit 9 (Day 162 ± 7 days) – End of Study (EOS) Visit

The following assessments will be conducted at this visit:

- Perform physical examination (excluding genitourinary system) including height and weight, and neurological examination
- Perform 12-lead ECG
- Record vital signs (pulse rate, BP, temperature, and RR)
- Collect blood samples for hematology and serum chemistry
- Collect urine sample for urinalysis and for pregnancy testing (FOCP only)
- Collect urine sample for drug screen
- Perform visual neurological exam
- Perform eye exam
- Administer C-SSRS
- Review and record concomitant medications
- Administer PedMIDAS, PedsQL 4.0 scales
- Perform cognitive assessment
- Record AEs
- Collect SM and assess adherence

5.1.7 Safety Follow-up Telephone Call (Weeks 24 through 26)

The following assessments will be made during this telephone contact, at 1 to 3 weeks following the EOS/ET visit:

- Review concomitant medications
- Record AEs
- Perform cognitive assessment ([Appendix 10.5](#))

6 STUDY VARIABLES AND ASSESSMENTS

6.1 Headache Diary– Preventive Therapies (Version 2.0)

The Headache Diary ([Appendix 10.2](#)) is the primary tool for collecting information about migraine headaches and will be used in the format recommended by the NINDS. The diary will serve as the primary source for the primary outcome measure of MMDs. The diary will be provided to caregivers in an electronic format as an application and uploaded on the caregivers' personal mobile device or on a dedicated locked mobile device in case the caregiver does not have a personal device. Reminder alarms will be programmed for diary completion and SM administration to ensure regular data entry and treatment compliance.

The caregiver will enter data with the subject's assistance every day during the Prospective Baseline Period and throughout the duration of treatment, regardless of whether they experienced a headache.

Subject's caregivers will be trained to complete a prospective 28-day headache calendar to document if a headache occurred. Based on the diagnostic criteria for migraine (ICHD-3), if the subject experienced a migraine headache as documented in the calendar, the diary will be completed to record headache specific and detailed information.

For any given headache day, the responder will include information about the timing of the attack (when the headache started and ended and whether or not it recurred within a 24-hour period), the location and severity of the pain, premonitory and aura symptoms (nausea, photophobia and phonophobia), rescue medications (if used, selected from a list), the impact of the headache on subject's daily activities, and treatment adherence after randomization. Severity of pain will be measured on a scale of 0 to 10, where 0 = No pain and 10 = The worst pain.

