Prospective Baseline Period (Visit 2, 4 weeks before Visit 3)

[figure not shown]
At Visit 2, the subject's parent or guardian will be asked to maintain a daily electronic Headache Diary (completed by the parent with the subject's assistance) in which they will record daily headache-associated symptoms and the duration and severity of all headaches. Rescue medication usage during the 28-day Prospective Baseline Period will also be recorded in the diary. Vital signs, concomitant medications, clinical laboratory tests, urine pregnancy test (FOCP only) and suicidality evaluation using the C-SSRS will be obtained at the visit.

Treatment Phase

Randomization (Visit 3, Day 1)

Upon completion of the Prospective Baseline Period, eligibility for randomization will be determined based on 1) the number of migraine episodes (must be 3-12 inclusive) during the Prospective Baseline Period, *and* 2) the number of total headache days (migraine and non-migraine; no more than 14 headache days) during the Prospective Baseline Period as observed and recorded using the Headache Diary.

All eligible subjects will be randomized in a blinded fashion by the interactive web response system (IWRS) in a 1:1 ratio of placebo or SPN-538. Subjects will receive a 4-week supply of their assigned study medication (SM). Safety evaluations including AEs, vital signs and suicidality evaluation (using the C-SSRS), eye examinations, concomitant medications, urine pregnancy test (FOCP only), headache disability, HRQoL, and cognitive assessments will be obtained at the visit. SM accountability and resupply will occur at each subsequent study visit.

Maintenance Period (Visits 6 to 8, Weeks 9 to 20)

Once the target dose or MTD is reached, treatment at that dose will continue for the 12 weeks of the maintenance period; up to one dose reduction will be allowed for safety

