3.3.3 Exclusion Criteria

1. Subjects with chronic migraine (>14 headache days per month), cluster headaches, or migraine aura without headache, and who are unable to distinguish migraines from other headache types.
2. Subjects with more than 14 headache days during the 28-day Prospective Baseline Period (based on the Headache Diary).
3. Have taken any disallowed migraine preventive medication including TPM within 14 days prior to the start of the Prospective Baseline Period; or used onabotulinumtoxinA (Botox[®]) within 3 months prior to entering the Screening period.
4. Previously failed to respond to TPM prophylaxis therapy using an adequate dose (2 to 3 mg/kg/day) for an adequate period of time (minimum of 3 months), or those who have previously discontinued TPM due to AEs within 6 months prior to Screening.
5. Previously failed more than 2 adequate clinical trials (defined as at least 1 month of treatment at a full therapeutic dose) of an established prophylactic anti-migraine regimen within 6 months prior to Screening.
6. Known history of allergic reaction or anaphylaxis to TPM.

7. Overuse of analgesic or migraine-specific agents for acute treatment of migraine defined as:
 - a. >10 treatment days/month of ergot-containing medications or triptans;
 - b. >15 treatment days/month with simple analgesics (including NSAIDs)
 - c. Use of narcotics
8. Subjects treated with the following prophylactic medications should discontinue the treatment 14 days prior to the Prospective Baseline Period: antipsychotics, antimanics, barbiturates, benzodiazepines amitriptyline, lithium, valproic acid, tricyclic antidepressants, AEDs, calcium channel blockers, sedatives, SSRIs, NSRIs, CGRP receptor antagonists, CBD oil, herbal preparations/supplements such as feverfew or St John's wort and/or any medications that could impair or decrease thinking and concentration. It is recommended to taper off antipsychotics, barbiturates, benzodiazepine, tricyclic antidepressants, lithium, amitriptyline, valproic acid, SSRIs and NSRIs as applicable.
Note: Subjects must refrain from using these medications throughout the duration of the study.
9. Subjects using non-pharmacologic complementary and alternative prophylactic approaches for migraine prevention, such as neuromodulation, acupuncture, behavioral interventions, spinal manipulation, occipital nerve block and neurofeedback.

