10.2 Headache Diary – Preventive Therapies (Version 2.0)

Instructions: This form should be completed by the participant for each day the participant/subject experienced a headache/migraine.

1. Did you experience a headache today? Yes No
2. What time did your headache start? (24 hour clock) Woke up with this headache
3. What time did your headache end? (24 hour clock) Headache resolved after falling asleep
4. What acute pain medication(s), in addition to the study drug, did you take? (Choose all that apply)

 Acetaminophen	 Ibuprofen
 Almotriptan	 Naproxen
 Aspirin	 Naratriptan
 Dihydroergotamine (DHE)	 Rizatriptan
 Eletriptan	 Sumatriptan
 Ergotamine tartrate (ET)	 Zolmitriptan
 Frovatriptan	 Other, specify:
5. Describe the worst severity of your headache today? Complete one of the following pain severity scales:
 - a. Which word describes the severity of your headache?
 None Mild Moderate Severe Very Severe (for cluster headaches)
 - b. Rate your overall worst pain for this headache on a scale of 0-10: ("0" = no pain & "10" = the worst pain): 0 1 2 3 4 5 6 7 8 9 10
6. Do any of the following describe your pain? (Choose all that apply)

 Throbbing	 Pressure
 Pounding	 Pulsating with the heart beat
 Stabbing	 Squeezing
 Constant	 Other, specify:
 Sharp	
7. Where is the location of your headache pain? (Choose one)
 Right Left Bilateral (both sides)
8. Where is the location of your headache pain that hurts the most? (Choose all that apply)

 Top	 All over
 One Eye (specify,  left  right)	 Right Temple
 Around Eyes	 Left Temple
 Behind Eyes	 Front
 Back	 Other, specify:
 Neck	

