### 5.2. Secondary Efficacy Variables

The secondary efficacy endpoints are:

1. Responder, defined as a subject with  $\geq 50\%$  reduction in the MMDs during the last 4 weeks of the Treatment Phase relative to Prospective Baseline Period.
2. Change from baseline in the monthly migraine-specific acute rescue medication use in the last 4 weeks of the Treatment Phase.

The 28-day rate of migraine-specific acute rescue medication (MED) days is calculated during the last 4 weeks of DBL period as

$$\frac{\# \text{ of days rescue MED used}}{\# \text{ of days with nonmissing headache record in the diary}} \times 28$$

The 28-day rate for the prospective baseline is calculated as in above during the 4 weeks

of ‘prospective baseline’.

3. Change in the monthly rate of total headache days (migraine and non-migraine), duration and severity.
  - a) Total headache days: The 28-day rate of total headache days and prospective baseline are calculated using the same formula as for the primary endpoint.
  - b) Duration of headache: The 28-day duration is calculated during the last 4 weeks of DBL period as

$$\frac{\text{sum of all headache duration}}{\# \text{of days with nonmissing headache record in the diary}} \times 28$$

The 28-day rate for the prospective baseline is calculated as in above during the 4 weeks of ‘prospective baseline’.

- c) Severity of headache: The 28-day rate for severity will be calculated for each headache incidence of severity category (mild, moderate, severe, and very severe). The 28-day rate for mild severity is calculated during the last 4 weeks of DBL period as:

$$\frac{\# \text{of days with mild headache incidence}}{\# \text{of days with nonmissing headache record in the Diary}} \times 28$$

The 28-day rate for the prospective baseline is calculated as in above during the 4 weeks of ‘prospective baseline’.

The 28-day rates of moderate, severe, and very severe headache days will be calculated similarly.

4. Onset of treatment effect, defined as the time to first statistically significant treatment effect observed and maintained until the end of study in the primary endpoint.
5. Change from baseline in the Total Headache Disability Score as measured by PedMIDAS during the last 4 weeks of the Treatment Phase.
6. Change from baseline in the HRQoL as measured by the PedsQL 4.0 Total Scale Score during the last 4 weeks of the Treatment Phase for the self-report and the parent-report.

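### Protocol 6.1 ties the detailed headache diary to an ICHD-3 migraine, against the rest of the protocol; applied literally, headache days and migraine days could be undercounted

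*Protocol*

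**What the plan says.** Protocol 6.1 names the Headache Diary as the source for monthly migraine days (MMDs). Its paragraphs describe completion in different ways.

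- Second paragraph: the caregiver enters data every day, "regardless of whether they experienced a headache".
- Third paragraph: caregivers are "trained to complete a prospective 28-day headache calendar to document if a headache occurred". It then applies ICHD-3: "if the subject experienced a migraine headache as documented in the calendar, the diary will be completed to record headache specific and detailed information".
- Fourth paragraph: "For any given headache day, the responder will include information about the timing of the attack", followed by severity, symptoms, rescue medication and impact.

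Elsewhere the scope is all headaches. Section 3.1 says of the baseline diary that "they will record daily headache-associated symptoms and the duration and severity of all headaches"; the Synopsis says the same, and the Section 3.1 maintenance text also covers all headaches. The form in Appendix 10.2 is instructed as follows: "This form should be completed by the participant for each day the participant/subject experienced a headache/migraine". Its Question 1 asks about any headache that day.

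The diary feeds three things that matter here: the 14-headache-day ceiling over the baseline period (inclusion 3, exclusion 2), the secondary endpoint on total headache days, duration and severity, and the MMDs. For total headache days, SAP 5.2 states: "The 28-day rate of total headache days and prospective baseline are calculated using the same formula as for the primary endpoint".

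**The concern.** The ICHD-3 sentence places a migraine judgement ahead of the detailed questions. The SAP works the other way round: section 4 takes the diary answers for any headache and derives migraine status from them. If the sentence is applied as written, the data needed to classify a headache are collected only after someone has already classified it.

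Two losses could follow. Non-migraine headaches would lack the entries that decide whether they count as Headache Days, which touches eligibility and a secondary endpoint. Headaches that the SAP would call migraine but ICHD-3 would not could have no detail at all, which touches the primary endpoint and the responder endpoint derived from it. Neither can be repaired at analysis, because the answers would never have been collected.

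**Working it through.** **The plan's own figures.** The documents state no figure for diary completeness by headache type. The sample size reproduces: 2 × (1.960 + 0.842)² × 3² / 1.1² = 2 × 7.85 × 9 / 1.21 = 116.8, so 117 per arm; 234 / 0.85 = 275.3, so 276 randomised. This point does not change it.

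**Step 1: the completion rules side by side.**

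| Place | When the detailed items are completed |
|---|---|
| Protocol 6.1, third paragraph | If a migraine headache by ICHD-3 |
| Protocol 6.1, fourth paragraph | Any headache day |
| Synopsis and Protocol 3.1 (baseline) | All headaches |
| Protocol 3.1 (maintenance) | All headaches |
| Appendix 10.2 instruction | Each headache or migraine day |

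The daily-entry rule in 6.1 fits with the last four rows as ordinary branching: Question 1 every day, the rest on a yes. Only the third paragraph of 6.1 does not fit.

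**Step 2: what a non-migraine headache needs in order to count.** Under Appendix 10.1 and SAP section 4 item 3, it makes a Headache Day only if it exceeds 30 minutes or was treated acutely. Start and end times are Questions 2 and 3 of the form, and medication is Question 4. The calendar, as 6.1 describes it, records whether a headache occurred. Occurrence alone does not settle Headache Day status, and it gives neither the duration nor the severity that secondary endpoint 3 uses.

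**Step 3: the ICHD-3 condition against the SAP algorithm.**

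| | ICHD-3 migraine without aura, as quoted in Appendix 10.1 | SAP section 4 item 5 |
|---|---|---|
| Duration | 2 to 72 hours in children, untreated or unsuccessfully treated | At least 60 minutes, or at least 30 minutes with medication |
| Pain features | Two of four | Two of four |
| Associated symptoms | Nausea or vomiting, or photophobia with phonophobia | Not required |

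An untreated 90-minute headache with two pain features is a migraine under the SAP and falls short of the quoted two-hour minimum. A headache longer than two hours with two pain features but no associated symptoms is also a SAP migraine and fails the quoted criteria. If either is screened out at the calendar, the algorithm has nothing to work on.

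**Step 4: illustration for the 14-day ceiling (assumed values).** Let M be migraine days, H other true Headache Days, and r the share of H whose qualifying detail is recorded, with M fully recorded. The documents give none of these, so r runs over its whole range from 0 to 1. Recorded headache days = M + r × H, and the child passes when r ≤ (14 − M) / H.

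| M, H (true total) | r = 1 | 0.75 | 0.5 | 0.25 | 0 | Passes when |
|---|---|---|---|---|---|---|
| 8, 8 (16) | 16 | 14 | 12 | 10 | 8 | r ≤ 6/8 = 0.75 |
| 12, 6 (18) | 18 | 16.5 | 15 | 13.5 | 12 | r ≤ 2/6 = 0.33 |

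Both children are ineligible on their true counts. At r = 1, which is the all-headache reading, nothing is lost. At r = 0, total headache days reduce to migraine days.

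**The case against.** The other side has a good case. The sentence in 6.1 does not contain the word only, and it does not say that other headaches are left out. The calendar in the same paragraph records any headache. Every other statement of scope, and the form itself, points to all headaches. The electronic branching is not shown. Caregivers are trained at Visit 2, sites review the diary at Visits 2 to 8, and the 14-day ceiling is also applied to the three months before Screening. All of this lowers the chance that non-migraine headaches were actually skipped.

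That stands as an argument about likelihood and size. It does not remove the contradiction. The calendar as described lacks the duration and medication entries, retrospective history does not replace the prospective baseline check, and a review of diary entries cannot restore detail that was never entered.

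A reader might infer three stronger things that the documents do not support.

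- That these endpoints are in fact undercounted. Nothing shows that the sentence governs the app or the sites.
- That the SAP rates are inflated because the denominator in SAP 5.1 and 5.2, days with a nonmissing headache record, could mean completed detailed forms. The daily-entry rule in 6.1 points against that reading, and SAP 6.7.1 on missing efficacy data, which might settle it, is listed in the contents but its text is not in the public copy.
- That the protocol disagrees materially on who answers. The participant wording in Appendix 10.2 and inclusion 8 differs from the caregiver-with-child wording in 6.1, but this is a minor matter of wording.

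**Conclusion.** The contradiction is real and sits in the section that governs the primary-endpoint instrument. Applied literally, the ICHD-3 sentence could undercount Headache Days for the 14-day ceiling, could undercount the total headache days, duration and severity endpoint, and could leave some SAP-defined migraines unclassified, so that MMDs are affected as well.

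The size cannot be computed from the documents. It depends on how often children have non-migraine or borderline headaches and on how the app and sites treat them, and neither is given. It is zero if the app already opens the detailed items for any headache. The counts in the illustration rest on assumed headache frequencies and show only how the ceiling could be passed. The step from the text to a loss also assumes that the caregiver, who completes the calendar, applies the ICHD-3 condition; that is a fair inference but is not stated. The case for correcting the sentence is that the change is cheap and any loss could not be recovered.

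**What to change.** Reword the third paragraph of Protocol 6.1 so that a yes to Question 1, for any headache, opens all detailed items. Remove the ICHD-3 migraine condition there, so that migraine status is derived only by the SAP section 4 algorithm. Confirm that the ePRO branching and the Visit 2 diary training match this.

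The cost is one wording change, a check of the app and, if needed, a retraining note. The downside is a small added entry burden on non-migraine headache days.
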